17.4.4 Procedures

17.4.4.1 Assessments

Self-Reported EQ-5Ds from Service Users

Consented SUs will be asked to complete the EQ-5D+C (a standard EQ-5D with one additional question for self-reported cognitive ability) with explanation from an independent researcher. The researcher will spend up to 10 minutes to gain a response from the subject. If their attempt proves unsuccessful, the subject will be categorised as unable to participate on that occasion and an explanation will be recorded by the researcher. These participants will be able to participate on another day if they wish, but will remain categorised as initially unable to participate.

If the SU is able to provide responses to the EQ-5D+C on this occasion, they will also be asked to complete the Mini-Mental State Examination (MMSE) by the researcher.

• Proxy EQ-5Ds from Carers and Frequent Visitors

If possible, on the same day, the carer [and most frequent visitor, if available onsite] will be asked to complete two versions of the EQ-5D proxy questionnaire: (i) how the proxy would rate the SU's health (EQ-5D: 1) and (ii) how the proxy thinks the SU would rate his/her own health (EQ-5D: 2). If the visitor is unavailable in person on that day, the researcher will attempt to contact them by telephone. The time between gathering data from each diad/triad should be kept to a minimum (max. 3 days). Proxies will be asked to respond retrospectively so that all EQ-5D reports refer to an SU's HRQoL at the same point in time.

Proxies will also be asked for a simple assessment of the SU's ability to complete the EQ-5D in the form of a 'yes/no' response.

Researcher Assessment of Cognitive Functioning

In addition to cognitive assessments of the SU, carer and frequent visitor, the researcher will also be asked to provide their own assessment of the SU's ability to complete EQ-5D on the day in the form of a 'yes/no' response.

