For the EQ-5D by Proxy study, the Care Home manager will be approached to give permission for the Care Home to take part in this sub study and for all Care Home Carers and residents to be approached about the sub study. The existing PAAD agreement will be amended to reflect their participation in the EQ5D Sub Study.

All assigned carers in each recruited home will be approached by the researcher, issued with an information sheet about the study, and asked to consent to take part. They will then be asked to identify all service users (SUs) they are assigned to. For each SU, the carer will be asked how long they have been their assigned carer, and if they consider each of their SUs to have general difficulties in their cognitive ability (i.e. competent or non-competent). The carer may ask the researcher any questions they wish about the study.

Each SU will be approached by the researcher, provided with an information sheet about the study, and asked to provide their consent to participate. Again, the SUs can ask any questions they have about the study and may discuss this with their carer, family and friends if they wish. If they do not wish to participate in the study, this will not affect the care they receive in any way. If they would like to participate but are unable to complete questionnaires due to physical difficulties, the researcher can help them by reading the questions and by noting their own responses if required. If they are unable to provide the researcher with consent due to cognitive difficulties, assent will be sought from their assigned consultee.

In this case, the consultee will be provided with an information sheet and asked to provide assent for their SUs participation in the study. If they are agreeable, the SU will be entered into the study.

In the event that SU cannot provide informed consent, when available, the most frequently visiting relative or friend of the consented/assented SU (known as **relative**) will be approached by the researcher, provided with an information sheet, and asked to provide their consent to participate in the study. If they wish to participate, it will then be possible to gather triad data for this SU (i.e. from SU, carer and relative). If the relative does not wish to participate, it will only be possible to gather diad data for this SU (i.e. from SU and carer).

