17.4.2 Sub Study Objectives

This exploratory sub-study is concerned with the hypothesis that there is an inverse relationship between agreement between SU and proxy EQ-5D scores and the SU's level of cognitive competence. If results support this hypothesis, then a minimum level of cognitive competence will be identified below which EQ-5D data should be administered by proxy. The study will also explore whether a

combination of professional and frequent visitor proxies would be preferable to either proxy alone.

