17.4.3.2 Recruitment of Participants

• Carers

All carers in each recruited home will be approached by the researcher, issued with an information sheet about the study, and asked to consent to take part. They will then be asked to identify all SUs they are assigned to. The carer may ask the researcher any questions they wish about the study.

Service Users

Each SU will be approached by the researcher, provided with an information sheet about the study, and asked to provide their consent to participate. Again, the SUs can ask any questions they have about the study and may discuss this with their carer, family and friends if they wish. If they do not wish to participate in the study, this will not affect the care they receive in any way. If they would like to participate but are unable to complete questionnaires due to physical difficulties, the researcher can help them by reading the questions and by noting their own responses if required. If they are unable to provide the researcher with consent due to cognitive difficulties, assent will be sought from their assigned consultee.

In this case, the consultee will be provided with an information sheet and asked to provide assent for their SU's participation in the study. If they are agreeable, the SU will be entered into the study.

Frequent Visitors

When available, the most frequently visiting relative or friend of the consented/assented SU will be approached by the researcher, provided with an information sheet, and asked to provide their consent to participate in the study. If they wish to participate, it will then be possible to gather triad data for this SU (i.e. from SU, carer and frequent visitor). If the visitor does not wish to participate, it will only be possible to gather dyad data for this SU (i.e. from SU and carer).

The frequent visitor will also be asked to provide details on the nature of their relationship to the SU (e.g. sister, brother, daughter, son, grandchild, friend, etc) and the frequency of their visits (e.g. number of visits weekly/monthly/annually).

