17.4.5 Sample size

There is no predetermined sample size, although the aim is to recruit as many SUs as possible from two of the larger residential care homes involved in the PAAD study, and their associated carers and frequent visitors. This sub-study may, therefore, include SUs who are not involved in the PAAD Randomised Controlled Study, but aims to include SUs with a broad range of cognitive functioning.

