17.4.6 Analysis

Given the relatively small sample and the exploratory nature of this sub-study, the results will be used to generate hypotheses rather than test them.

Agreement in overall EQ-5D scores between proxies and the SU will be assessed using the Bland/Altman method to estimate 95% limits of agreement.

As data on the individual EQ-5D dimensions are trichotomous (score = 1, 2 or 3) we will use a Kappa statistic to examine agreement between scores obtained from a relative and carer for both SU/proxy on each dimension.

We will also use a Kappa statistic to examine agreement between the carer, research nurse and SU's assessment of the SUs cognitive ability on the day and, via ANOVA, will explore differences between the average MMSE scores and those who said 'yes' or 'no' regarding the SU's level of cognitive ability.

While disagreement between responses by any subject and his/her proxies can clearly be due to factors other than cognitive impairment, it is still anticipated that on average, the level of agreement in each of the above analyses will get closer to the level of agreement for a 'clearly cognitively competent' sub-group alone. These results will allow exploration of the MMSE score below which EQ-5D data should be collected by proxy in the RCT.

Ethics approval

This sub-study is classified as a substantial amendment to the main PAAD study.

18 References

- 1. Havenaar, R.H.I.t., Veld JHS, *Probiotics: a general view.* The Lactic Acid Bacteria in Health and Disease, 1992: p. 1 200.
- Surawicz, C.M., Probiotics, antibiotic-associated diarrhoea and Clostridium difficile diarrhoea in humans. Best Practice & Research Clinical Gastroenterology, 2003. 17(5): p. 775-783.
- 3. Parkes, G.C., J.D. Sanderson, and K. Whelan, *The mechanisms and efficacy of probiotics in the prevention of Clostridium difficile-associated diarrhoea.* Lancet Infect Dis, 2009. **9**(4): p. 237-44.
- 4. Fletcher, K.R. and M. Cinalli, *Identification, Optimal Management, and Infection Control Measures for Clostridium difficile-Associated Disease in Long-Term Care.* Geriatric Nursing, 2007. **28**(3): p. 171-181.
- 5. Monaghan, T., T. Boswell, and Y.R. Mahida, *Recent advances in Clostridium difficile-associated disease.* Gut, 2008. **57**(6): p. 850-860.
- 6. Nelson, R., *Antibiotic treatment for clostridium difficile-associated diarrhea in adults (Review).* The Cochrane Collaboration, 2007(3).

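### Sub-study 4 takes no MMSE from residents who never complete the EQ-5D+C, and protocol sections 14.1 and 17.4.3.2 disagree on whose visitors are approached

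*Protocol*

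**What the plan says.** **MMSE.** Section 17.4.4.1 of the protocol gives the rule: "If the SU is able to provide responses to the EQ-5D+C on this occasion, they will also be asked to complete the" MMSE. The summary of sub-study 4 in section 4 says the same. Of residents who do not manage the EQ-5D+C, section 17.4.4.1 says: "These participants will be able to participate on another day if they wish, but will remain categorised as initially unable to participate". It provides no MMSE for those who never respond.

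**Use of the MMSE.** Section 17.4.2 states that, if the hypothesis is supported, "then a minimum level of cognitive competence will be identified below which EQ-5D data should be administered by proxy". Section 17.4.6 names the scale: "These results will allow exploration of the MMSE score below which EQ-5D data should be collected by proxy in the RCT". The same section plans an ANOVA of mean MMSE between those answering yes and no on the resident's cognitive ability. Section 17.4.5 says that the sub-study "aims to include SUs with a broad range of cognitive functioning".

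**Visitors.** Section 14.1 opens its rule with a condition: "In the event that SU cannot provide informed consent, when available, the most frequently visiting relative or friend of the consented/assented SU" will be approached. Section 17.4.3.2 has no such condition: "When available, the most frequently visiting relative or friend of the consented/assented SU will be approached by the researcher". The procedures in 17.4.4.1 carry none either: "the carer [and most frequent visitor, if available onsite] will be asked to complete two versions of the EQ-5D proxy questionnaire".

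**The concern.** The sub-study is meant to inform at what MMSE score a proxy should answer for the resident in the Stage 2 trial. Residents who cannot answer for themselves are those for whom a proxy is unavoidable, and the protocol does not measure MMSE in them. The MMSE comparison by rated ability then draws its 'no' group only from residents who were rated unable but completed the questionnaire anyway. For the researcher's own rating of ability on the day, that group could be very small. A statistical analysis plan cannot repair this, because the scores are never collected.

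The second aim is to learn whether a carer and a visitor together serve better than either alone. Judging both against the resident's own answers across cognitive levels needs residents with a self-report, an MMSE, a carer proxy and a visitor proxy. If visitors are approached only for residents who cannot consent, few residents will have all four.

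**Working it through.** The protocol gives no power, precision or completion figure for sub-study 4 (17.4.5 sets no predetermined sample size), so there is nothing to reproduce. The check is a comparison of the passages, followed by an illustration of size.

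**1. Which analyses need which data**

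| Analysis (17.4.6) | Needs | Effect of the MMSE condition |
|---|---|---|
| Bland/Altman limits, resident v proxy | Resident's own EQ-5D and a proxy EQ-5D | None: a non-completer has no self-report to compare |
| Kappa by EQ-5D dimension, resident v proxy | As above | None |
| ANOVA of MMSE by yes/no ability | MMSE and a rating | 'No' group lacks everyone who never completed |
| MMSE score below which a proxy is used | MMSE over the low range | Low end seen only in residents who completed |

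**2. Residents without an MMSE.** N = 150 (approximate, 17.4.3). The share u who never complete the EQ-5D+C is assumed.

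With MMSE = N(1 − u); without = N·u.

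| u | With MMSE | Without |
|---|---|---|
| 10% | 135 | 15 |
| 30% | 105 | 45 |
| 50% | 75 | 75 |
| 70% | 45 | 105 |

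**3. Residents with self-report, MMSE, carer proxy and visitor proxy.** All inputs other than N are assumptions:
- v = 50%, visitor uptake
- b = 90%, completion of the EQ-5D+C among residents who can consent
- c = 30%, 50% or 70%, share unable to consent
- a = 0%, 10% or 30%, completion among those unable to consent

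Carer and MMSE data are taken as complete for those who self-report.

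Under 14.1: N·v·c·a. Under 17.4.3.2: N·v·[c·a + (1 − c)·b].

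Example with c = 50%, a = 10%: 14.1 gives 150 × 0.5 × 0.5 × 0.1 = 3.75; 17.4.3.2 gives 150 × 0.5 × (0.05 + 0.45) = 37.5.

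| c | a | Under 14.1 | Under 17.4.3.2 |
|---|---|---|---|
| 30% | 0% | 0 | 47.25 |
| 30% | 10% | 2.25 | 49.5 |
| 30% | 30% | 6.75 | 54.0 |
| 50% | 0% | 0 | 33.75 |
| 50% | 10% | 3.75 | 37.5 |
| 50% | 30% | 11.25 | 45.0 |
| 70% | 0% | 0 | 20.25 |
| 70% | 10% | 5.25 | 25.5 |
| 70% | 30% | 15.75 | 36.0 |

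The range is about 0 to 16 under 14.1 and 20 to 54 under 17.4.3.2. The difference is N·v·(1 − c)·b, that is 47.25, 33.75 or 20.25 residents for c = 30%, 50% or 70%, whatever a is.

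**The case against.** The strongest reply is that the planned cut-off rests on agreement. The hypothesis links resident/proxy agreement to cognitive competence, and agreement requires the resident's own EQ-5D. A non-completer could not contribute even with an MMSE. This stands: the condition costs the agreement analyses nothing, and resident/carer agreement over the MMSE range of completers remains available.

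A reader might infer that no MMSE can ever be tied to inability. That goes too far. Residents may try again on another day while still counted as initially unable, and a successful later attempt can reasonably be read as leading to an MMSE. Cognitive information is not wholly absent either: under 14.1 carers class each of their residents as competent or not, and under 17.4.4.1 proxies and the researcher give yes/no ability ratings with no stated restriction.

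A reader might also infer that visitor data for residents with capacity are lost. The documents show only a conflict. The sentence in 14.1 is itself inconsistent, since it speaks of a resident who cannot consent and then of one who has consented or been assented. The sub-study's own recruitment section, its design statements (sections 4 and 17.4.3) and its procedures set no capacity condition. Under those there is no such loss, and carer proxies are unaffected under either reading.

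Finally, section 17.4.6 declares the work exploratory and hypothesis-generating. That lowers the weight. It does not remove the point, because sections 3.2 and 17.4.2 still say that a minimum level will be identified if the hypothesis is supported, and section 11.2 lists identifying it among the Stage 1 feasibility components.

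**Conclusion.** The point holds in a limited form. Residents who never complete the EQ-5D+C have no MMSE, so the comparison of MMSE by rated ability is selectively incomplete in its 'no' group, and the low end of any MMSE cut-off is poorly observed. Sections 14.1 and 17.4.3.2 contradict each other on visitors, and the comparison of proxy types would suffer if 14.1 were followed.

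The documents do not support saying that the data for a cut-off or for comparing proxies are removed altogether. The agreement analyses among completers are intact, and the visitor loss depends on which section staff follow.

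The sizes (15 to 105 residents without an MMSE; about 0 to 16 against 20 to 54 residents with all four data items) are illustrations on assumed shares, not forecasts. The text of the Appendix 8 flow diagram as available ends after the first carer steps, so its MMSE and visitor steps could not be compared with these sections.

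**What to change.** In section 4 and section 17.4.4.1, attempt the MMSE in every consented or assented resident, whatever the outcome of the EQ-5D+C. Record an incomplete attempt as incomplete, with the reason (cognitive, sensory or physical, refusal). Do not score it as zero, which would mix cognitive failure with other causes and distort any cut-off. In sections 12.2 and 17.4.6, add a description of MMSE by able or unable to complete the EQ-5D+C.

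In section 14.1, remove the opening condition on inability to consent so that the visitor rule matches 17.4.3.2, and check that the Appendix 8 diagram agrees with both.

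The cost is one short extra assessment for each non-completer, with an instrument already in use and a researcher already present. Some attempts will be incomplete. The number is not known from the protocol; on the range above it is 15 to 105. The change to 14.1 is one clause.

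The change has to be made before data collection, because MMSE scores not taken at the time cannot be recovered later.

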17.4.5 Sample size

There is no predetermined sample size, although the aim is to recruit as many SUs as possible from two of the larger residential care homes involved in the PAAD study, and their associated carers and frequent visitors. This sub-study may, therefore, include SUs who are not involved in the PAAD Randomised Controlled Study, but aims to include SUs with a broad range of cognitive functioning.

17.4.6 Analysis

Given the relatively small sample and the exploratory nature of this sub-study, the results will be used to generate hypotheses rather than test them.

Agreement in overall EQ-5D scores between proxies and the SU will be assessed using the Bland/Altman method to estimate 95% limits of agreement.

As data on the individual EQ-5D dimensions are trichotomous (score = 1, 2 or 3) we will use a Kappa statistic to examine agreement between scores obtained from a relative and carer for both SU/proxy on each dimension.

We will also use a Kappa statistic to examine agreement between the carer, research nurse and SU's assessment of the SUs cognitive ability on the day and, via ANOVA, will explore differences between the average MMSE scores and those who said 'yes' or 'no' regarding the SU's level of cognitive ability.

While disagreement between responses by any subject and his/her proxies can clearly be due to factors other than cognitive impairment, it is still anticipated that on average, the level of agreement in each of the above analyses will get closer to the level of agreement for a 'clearly cognitively competent' sub-group alone. These results will allow exploration of the MMSE score below which EQ-5D data should be collected by proxy in the RCT.

Ethics approval

This sub-study is classified as a substantial amendment to the main PAAD study.

18 References

- 1. Havenaar, R.H.I.t., Veld JHS, *Probiotics: a general view.* The Lactic Acid Bacteria in Health and Disease, 1992: p. 1 200.
- Surawicz, C.M., Probiotics, antibiotic-associated diarrhoea and Clostridium difficile diarrhoea in humans. Best Practice & Research Clinical Gastroenterology, 2003. 17(5): p. 775-783.
- 3. Parkes, G.C., J.D. Sanderson, and K. Whelan, *The mechanisms and efficacy of probiotics in the prevention of Clostridium difficile-associated diarrhoea.* Lancet Infect Dis, 2009. **9**(4): p. 237-44.
- 4. Fletcher, K.R. and M. Cinalli, *Identification, Optimal Management, and Infection Control Measures for Clostridium difficile-Associated Disease in Long-Term Care.* Geriatric Nursing, 2007. **28**(3): p. 171-181.
- 5. Monaghan, T., T. Boswell, and Y.R. Mahida, *Recent advances in Clostridium difficile-associated disease.* Gut, 2008. **57**(6): p. 850-860.
- 6. Nelson, R., *Antibiotic treatment for clostridium difficile-associated diarrhea in adults (Review).* The Cochrane Collaboration, 2007(3).

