17.4.3 Design

This is an observational sub study involving approximately 150 service users, their main carer and their most frequent visitor. (Please see *Figure 1* for a diagram of the study protocol).

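### Sub-study 4 asks how carer and visitor proxies differ, but its stated analysis of the overall EQ-5D score neither compares them on the same residents nor assesses the combined proxy

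*Protocol*

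**What the plan says.** The title of sub-study 4 in Protocol 1.1 presents it as exploring differences between proxy types. Sections 3.2 and 17.4.2 add the question of whether a "combination of professional and frequent visitor proxies" is better than either proxy by itself. Section 17.4.1 explains that Stage 2 will use EQ-5D and needs the most reliable proxy.

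For the overall score, 12.2 and 17.4.6 give the same single method: "Agreement in overall EQ-5D scores between proxies and the SU will be assessed using the Bland/Altman method to estimate 95% limits of agreement". A further sentence applies kappa to the individual dimensions. It names relative and carer together, but does not make clear whether they are compared with each other or each with the resident. No analysis of a combined proxy is named.

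On who supplies ratings, 17.4.3.2 says that if the visitor declines, "it will only be possible to gather dyad data for this SU (i.e. from SU and carer". That section has the visitor approached for any resident who has entered by consent or assent. The parallel text in 14.1 opens with the condition that the resident is unable to give informed consent.

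On status, 17.4.6 says that "the results will be used to generate hypotheses rather than test them".

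**The concern.** The question is comparative, and the design is well suited to it: in a triad, carer and visitor rate the same resident. The stated analysis does not use that. It measures agreement between proxies and the resident and does not say on which residents the two proxy types are to be set against each other.

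The natural default is every available pair. Carer limits would then come from dyads and triads, and visitor limits from triads only. The visitor set is nested in the carer set but is not a copy of it. If visited residents are harder (or easier) to rate, one proxy will look worse (or better) for reasons unrelated to the proxy.

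The sub-study's own hypothesis is that agreement varies with cognition. If 14.1 governs, having a visitor rating is itself tied to cognition, so proxy type would be confounded with the factor under study. At stake is a descriptive result meant to inform the use of proxies in Stage 2.

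**Working it through.** **1. Inputs.** Section 17.4.3 gives the size: "This is an observational sub study involving approximately 150 service users, their main carer and their most frequent visitor". Section 17.4.5 says "There is no predetermined sample size". The protocol gives no SD, share of triads, carer caseload or correlation between proxies, so there is no planned figure to reproduce. Everything below except the 150 is an assumption.

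**2. Which residents enter each set of limits.**
- Carer minus resident: dyads and triads.
- Visitor minus resident: triads only.
- Triads under 17.4.3.2: any participating resident with an available, willing visitor.
- Triads under 14.1, read literally: only residents who cannot give informed consent.

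**3. Effect of case mix on the limits.** Let both proxies be equally good. Let *s* be the SD of proxy-minus-resident differences in competent residents, *ks* the SD in impaired residents, and *p* the share impaired, with the same mean difference in both groups.

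- SD over all residents = s × √[(1 − p) + p k²]
- SD if visitors rate impaired residents only = k s
- Ratio of visitor to carer limits: R = k / √[(1 − p) + p k²]

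Take s = 0.2 and p = 0.5 (R does not depend on s):

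| k | Carer limits, all residents | Visitor limits, impaired only | R |
|---|---|---|---|
| 1 | ±1.96 × 0.200 = ±0.39 | ±0.39 | 1.00 |
| 1.5 | ±1.96 × √(0.5×0.04 + 0.5×0.09) = ±1.96 × 0.255 = ±0.50 | ±1.96 × 0.3 = ±0.59 | 1.18 |
| 2 | ±1.96 × √(0.5×0.04 + 0.5×0.16) = ±1.96 × 0.316 = ±0.62 | ±1.96 × 0.4 = ±0.78 | 1.26 |

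If triads are a random subset, R = 1 for every k. If the comparison is confined to triads, both proxies have the same limits (±0.59 or ±0.78) and the gap disappears.

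The direction is also an assumption. Section 17.4.2 literally states an inverse relation between agreement and competence. If agreement were better in impaired residents, k would be below 1, R would fall below 1, and the spurious gap would favour visitors.

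**4. Does carer clustering matter?** Carers may rate several residents: "They will then be asked to identify all SUs they are assigned to". With m residents per carer and intraclass correlation ICC, the limits change in width by √[1 − ICC(m − 1)/(N − 1)]. For N = 150, m = 3 to 10 and ICC = 0.05 to 0.30:
- Limits: √(1 − 0.05×2/149) = 0.9997 to √(1 − 0.30×9/149) = 0.991, a change of under 1%.
- Standard error of the mean bias, if one were reported: too small by √[1 + (m − 1)ICC], from √1.10 = 1.05 to √3.70 = 1.92.

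Clustering therefore leaves the planned limits almost untouched. It would matter only for a confidence interval.

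**The case against.** The strongest reply is that the sub-study is small and hypothesis-generating, and that the residents used for each comparison can be set in an analysis plan that is not shown here. The visitor set lies wholly inside the carer set, so it is too strong to say that different residents are compared. The kappa sentence, if read as direct carer–relative agreement, can only be computed in triads. The condition in 14.1 may be unintended, since the same sentence goes on to treat the resident as consented or assented. Residents who cannot complete the EQ-5D themselves give no pair for either proxy, which limits how impaired the visited group can be. All of this stands and keeps the severity low.

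It does not remove the point. The protocol states its method for the overall score twice, and in neither place does that method answer the proxy-type or combined-proxy question. Direct carer–relative kappa would show whether the proxies agree with each other, not which is closer to the resident.

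Three stronger readings are tempting, and the text supports none of them:
- A reader might infer that linked ratings will be analysed as independent. The protocol is silent on this.
- A reader might infer that the error bars will be wrong. Section 17.4.6 names no confidence interval, standard error or carer-versus-visitor test, and clustering barely moves the limits themselves.
- A reader might infer that the ANOVA, which is to "explore differences between the average MMSE scores and those who said 'yes' or 'no", pools several raters and so counts each resident's MMSE more than once. It can equally be run separately for each rater.

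**Conclusion.** The point holds as a low-severity improvement. The overall-score analysis in 12.2 and 17.4.6 does not make the proxy comparison within residents and names no analysis of the combined proxy, although both belong to the sub-study's aims. With all available pairs, equally good proxies could show a gap in limits of 0% (random triads) or 18% to 26% (visitors for impaired residents only, half of residents impaired, SD ratio 1.5 to 2). These are illustrations. The protocol gives no figure that fixes the selection or the SD ratio, and the sign depends on how agreement varies with cognition. The conflict between 14.1 and 17.4.3.2 is in the text and decides how far visited residents are a selected group. No decision rule rests on these limits, but exploratory status does not remove case-mix bias from a comparison meant to inform Stage 2.

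**What to change.** In 17.4.6 and 12.2:
1. Compare the proxy types in triads only, as a paired within-resident contrast of carer-minus-resident with visitor-minus-resident. Use the differences for bias, and the absolute or squared differences for spread.
2. Assess the combined proxy, for example the mean of the two scores, on the same triads.
3. Report carer limits from all residents with a carer pair separately, as description only.
4. If confidence intervals are given for carer-based agreement, allow for residents nested in carers. This needs a carer identifier on each proxy form.

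Reconcile 14.1 with 17.4.3.2 on whose visitor is approached.

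The cost is analysis wording, plus fewer residents in this one comparison. If half of 150 residents were in triads (assumed), the 95% half-width for a carer limit, 1.96 × SD × √[1/N + 1.96²/(2(N − 1))], would rise from 0.27 SD at N = 150 to 0.39 SD at N = 75. Visitor limits rest on triads in any case. Pairing gives some precision back: for a correlation of 0.2 to 0.7 between the two proxies' differences (assumed, with equal variances), the standard error of the bias contrast is √(1 − r) = 0.89 to 0.55 of its value for two independent groups of the same size.
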